7.7. Schedule of Events

□Procedure/Assessment	Screening		12-24 hours before start of resection	Day of Resection	1 month @ +/-7 days	3 months [@] +/-7 days	6 months +/-14 days	12 months + /- 14 days
Initial eligibility assessment	Х							
Informed consent		Х						
Jrine pregnancy test ^f		Х						
Eligibility confirmation [^]		Х						
Demographics ^{&}		Х						
Staging information		Х						
Fumour subtype/size/location		Х						
Concomitant medications		Х						
EQ-5D #		Х			X@	X@	X@	X@
ress ^{\$}		Х			X@	X@	X@	X@
Randomisation		Х						
CG intravenous injection (*If randomised to ntervention arm)			X*					
Resection				Х				
Surgeon eCRF %				Х				
Margin status							Х	
Complications				Х	Х		Х	Х
Adverse Events (see section 9.2)				Х	Х		Х	
SAE Check				Х	Х		Х	Х
Survival status								Х
Cause of death if applicable								Х

follicle stimulating hormone (FSH) level in the postmenopausal range may be used to confirm a post-menopausal state in women not using hormonal contraception or hormonal replacement therapy. However, in the absence of 12 months of amenorrhea, a single FSH measurement is insufficient.

Interventional Non-CTIMP Protocol Template; version 1.0; dated 14 September 2015 [IRAS Number]

[^]Eligibility confirmation must be documented in the medical notes by a clinician delegated to the trial. This can be done one of three ways by the clinician delegated to the trial: 1) as a written entry in the patient's medical notes which includes confirmation that all criteria have been met and references the current version and date of the protocol, 2) by completing the eligibility checklist on paper and filing it in the patient's medical notes or 3) by completing the eligibility checklist on the Sealed Envelope database.

[&]Demographic data will be collected at screening and baseline and will include age, sex at birth, height, weight, ethnicity, smoking status, diagnosis of diabetes and postcode. [@] To be conducted remotely via ePRO

EQ-5D -Age on day of baseline assessments – continue using the same version of the questionnaire throughout the trial.

FOR 16+: EQ-5D-5L FOR 8–15-year-olds: EQ-5D-Y FOR 4-7-year-olds: EQ-5D-Y Proxy version 1 completed by a parent or carer.

^s TESS – Only to be completed for participants undergoing extremity limb salvation resections. There is a separate **upper** and **lower** extremity questionnaire, please use the correct one for the participant. **FOR 7–17-year-olds**: there is a paediatric version of each questionnaire to be used.

 $^{
m \%}$ Can be completed directly on database by surgeon or can be completed on paper and transcribed.

SarcoSIGHT

7.8. Withdrawal Criteria

Participants have the right to withdraw from the trial at any time without giving a reason. Investigator sites should try to ascertain the reason for withdrawal and document this reason within the eCRF and participants' medical notes.

The Investigator may discontinue a participant from the trial at any time if the Investigator considers it necessary for any reason including:

- Symptomatic deterioration
- Participant withdrawal of consent
- Significant protocol deviation or non-compliance
- Investigator's discretion that it is in the best interest of the participant to withdraw
- An adverse event that requires discontinuation of the trial intervention or renders the participant unable to continue in the trial
- Termination of the clinical trial by the sponsor

Participants who withdraw from the trial prior to intervention will be replaced, whilst those withdrawing following the procedure will not.

7.9. Storage and Analysis of Samples

It is the responsibility of the trial site to ensure that samples are appropriately labelled in accordance with the trial procedures to comply with the Data Protection Act (DPA). Biological samples collected from participants as part of this trial will be transported, stored, accessed, and processed in accordance with national legislation relating to the use and storage of human tissue for research purposes and such activities shall at least meet the requirements as set out in the 2004 Human Tissue Act and 2006 Human Tissue (Scotland) Act.

7.10. End of Trial

The end of the trial will be defined as completion of data collection after LPLV or completion of the transfer and analysis of samples and near infrared images associated with exploratory objectives, whichever comes latest.

8. TRIAL INTERVENTION

8.1. Name and Description of Interventions

8.1.1. Control arm

Patients randomised to standard of care will undergo surgical resection without pre-operative ICG administration or intra-operative fluorescence guidance. This will be performed as per the preferences of the operating surgeon but will be planned based on pre-operative imaging of the tumour, with appropriate skin mark-up.

SarcoSIGHT version 5.0 dated 25 June 2024

8.1.2. Intervention arm

The protocol for FGS using ICG is summarised in Section 16.3, Appendix 3. Prior to being able to recruit patients to the trial, surgeons must have completed training in FGS using ICG (see Section 8.4. Surgeon Training) Patients randomised to the FGS arm will be administered 1mg/kg ICG intravenously 12-24 hours prior to the procedure. Reconstitution of ICG will be done in line with the manufacturer's patient information leaflet provided in the pack. However, a dosing reference table document will be provided to site to aid staff in reconstitution of the drug. The skin will be marked based on pre-operative imaging as per standard of care and prepped using chlorhexidine to reduce background fluorescence from iodine-based solutions. The surgeon should then proceed with their planned resection as per standard of care. As they proceed with the resection they must use the Stryker SPY-PHI camera to image areas of interest; interpretation of images and any influence on operative decision making is at the discretion of the operating surgeon. If fluorescence changes the procedure at any time, further images (in white light, overlay mode, SPY fluorescence mode and colour segmented overlay mode) should be taken as appropriate. Following the resection, both the resected specimen and the wound bed should be imaged (in all modes as above), and a decision made regarding the requirement for the removal of any further tissue. Following reconstruction and closure, the operating surgeon must complete the trial Surgery CRF, stating whether, and if so at what point and how, fluorescence guided the procedure and changed decision making, as well as documenting the images taken. These pseudonymised images will be removed from the camera at site immediately after surgery by a member of the research team. Access to images will be restricted to delegated members of staff only and the location of the images will be monitored via a tracking log. It is essential that no personal identifiable data is included with the images on the camera stack or while in transfer. The images will be sent to the database team at NCTU and later transferred to collaborators at University College Dublin for exploratory analysis.

8.1.3. Margins

Following surgeries in the control arm and the intervention arm, the surgeon must confirm on the CRF and in the participant's clinical notes whether they believe the full tumour was resected or whether they are expecting an acceptable close/positive margin. Resected specimens should then be sent to the pathology laboratory to undergo trimming and margin assessment by a histopathologist as per standard practice. Once the pathology report is available and discussed at the MDT, the surgical team will complete a pathology specific trial report form, documenting the margin status. In the case of a UPM, plans for re-excision should also be documented, and the results of this also added to the 6- month follow up eCRF. It is important to note that a single case may have both acceptable and unexpected positive margins if a positive margin is present in an area not adjacent to the preserved structure; in this case it should be recorded as a UPM.

8.2. Schedule & Modifications

Patients will be discussed in the MDT and operated on at a time deemed appropriate by the treating team. No modification to the imaging protocol described in section 8.1.2. is allowed, although the interpretation of this imaging, and any decisions made as such, is at the discretion of the operating surgeon.

8.2.1. Known Risks of ICG

- o Anaphylaxis (especially in those with iodine or shellfish allergies)
- Urticaria
- Cough
- o Nausea
Interventional Non-CTIMP Protocol Template; version 1.0; dated 14 September 2015 SarcoSIGHT

- o Itch
- \circ Rash

8.2.2. Known Risks of Surgery

- o Pain
- \circ Infection
- o Bleeding
- o Scar
- o Stiffness
- Deep Vein Thrombosis/ Pulmonary Embolism
- o Damage to nerves/vessels
- Recurrence
- Need for further procedure(s)
- Further risks specific to the planned procedure

8.3. Concomitant Medications & Therapies

Participation in another interventional clinical trial in the 30 days preceding surgery are permitted.

All neo-adjuvant treatment regimens are permitted.

The class of concomitant medications that need to be reported are:

- o Tyrosine kinase inhibitors
- o Immunotherapy

8.4. Surgeon Training

Surgeons taking part in this trial will have different levels of experience in performing surgeries with FGS using ICG. As such there is a flexible approach to training surgeons which will include the following elements. To complete their training each surgeon will, at a minimum, have:

- 1. Participated in at least one FGS using ICG alongside a trained surgeon.
- 2. Watched the training video for FGS using ICG which includes a step-by-step recording of the procedure.
- 3. Completed a questionnaire to confirm they feel competent to perform FGS using ICG.

Surgeons who do not feel competent in the procedure can repeat steps 1 and 2 until they are satisfied, they can effectively perform FGS using ICG.

9. SAFETY REPORTING

9.1. Definitions

Table 2. Terms and definitions used in safety reporting for a non-CTIMP trial.

Term	Definition		
Adverse Event (AE)	Any untoward medical occurrence in a participant, including occurrences which are not necessarily caused by or related to the intervention under study.		
Adverse Reaction (AR)	An untoward or unintended response in a participant to which is related to the intervention under study i.e., that a causal relationship between the trial intervention and an AE is at least a reasonable possibility and the relationship cannot be ruled out. All cases judged by either the reporting medically qualified professional or the Sponsor as having a reasonable suspected causal relationship to the trial intervention qualify as adverse reactions.		
Serious Adverse Event (SAE)	 A serious adverse event is any untoward medical occurrence that: Results in death Is life-threatening* Requires inpatient hospitalisation or prolongation of existing hospitalisation Results in persistent or significant disability/incapacity Consists of a congenital anomaly or birth defect Other important medical events that jeopardise the participant or require intervention to prevent one of the above consequences * - life-threatening refers to an event in which the participant was at immediate risk of death at the time of the event; it does not refer to an event which hypothetically might have caused death if it were more severe. 		
Related Serious Event (RSE)	Any serious event that is classed in nature as serious, where there is evidence to suggest there is a causal relationship between the event and the trial procedures/intervention.		
Unexpected Related Serious Event (URSE)	Any SAE that is classed in nature as serious, where there is evidence to suggest there is a causal relationship between the event and the trial procedures/intervention, where the event is unexpected.		

9.2. Recording AEs

AEs will be recorded for surgery and ICG intravenous injection separately.

AEs related to surgery will not be collected directly via an AE form but instead via the complications eCRF. Complications will be recorded from day of surgery, at the 1-, 6- and 12-month follow-up visit. Any complications that are collected that also meet the criteria for an SAE, the site will complete an SAE form. Complications will be graded using the Calvien-Dindo Classifications of Surgical Complications system ³³ (see Section 16.4, Appendix 4).

Only AEs related or possibly related to the ICG intravenous injection (that take place within 72 hours of ICG intravenous injection) will be recorded in the AE eCRF. The research team will check the records on the day of resection, 1- and 6-month follow-up to check these have been reported if they have occurred. If the AE meets the criteria for an SAE, the site will complete an SAE form.

All SAEs will be recorded in the database.

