7.4. Blinding

Participants and operating team will not be blinded to the trial intervention due to the requirement for the administration of ICG to the participant and the use of extra technology during the procedure by the operating team. The histopathology staff and senior trial statistician will be blinded and unaware of the surgery type to allow for blinded measurement and analysis of primary outcome. The trial statistician will not be blinded.

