	16.3 Appendix 3- (yellow text box)	
	Removal of reference to 'unencrypted USB from yellow text be	ox.
	Throughout Sections	
	 Change from 'anonymised' to 'pseudonymised' Correction of grammar and typographical errors 	

All amendments to the protocol, substantial or non-substantial, are listed in this table. Substantial amendments have been approved by the NHS REC. Non-substantial amendments have been sent to the NHS REC for acknowledgement only.

Grade	Description
Grade I	Any deviation from the normal post-operative course not requiring surgical, endoscopic, or radiological intervention. This includes the need for certain drugs (e.g., antiemetics, antipyretics, analgesics, diuretics, and electrolytes), treatment with physiotherapy and wound infections that are opened at the bedside
Grade II	Complications requiring drug treatments other than those allowed for Grade I complications; this includes blood transfusion and total parenteral nutrition (TPN)
Grade III	Complications requiring surgical, endoscopic, or radiological intervention
Grade IIIa	Intervention not under general anaesthetic
Grade IIIb	Intervention under general anaesthetic
Grade IV	Life-threatening complications: this includes central nervous system complications (e.g., brain haemorrhage, ischaemic stroke, subarachnoid haemorrhage) which require intensive care, but excludes transient ischaemic attacks (TIAs)
Grade IVa	Single-organ dysfunction (including dialysis)
Grade IVb	Multi-organ dysfunction
Grade V	Death of the patient

Page **59** of **59**

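### Section 9.2 sorts early events by suspected cause onto a form that only FGS patients can have, so the between-arm complication comparison could be biased towards FGS

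*Protocol*

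**What the plan says.** Protocol section 9.2 sets up two recording routes: "AEs will be recorded for surgery and ICG intravenous injection separately".

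- **Surgery route, both arms:** "AEs related to surgery will not be collected directly via an AE form but instead via the complications eCRF".
- **ICG route:** the AE eCRF receives "Only AEs related or possibly related to the ICG intravenous injection (that take place within 72 hours of ICG intravenous injection").

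Section 8.1.2 has FGS patients "administered 1mg/kg ICG intravenously 12-24 hours prior to the procedure". Section 8.1.1 states the control condition: "Patients randomised to standard of care will undergo surgical resection without pre-operative ICG administration". Section 7.4 says "Participants and operating team will not be blinded to the trial intervention", and section 9.5.1 gives the causality judgement to the PI or delegate at site.

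Section 3.2.2 gives examples of complications and adds a catch-all for anything else the PI regards as a complication of the surgery. The grading table in Appendix 4 starts at Grade I, which covers minor departures from the usual post-operative course: "This includes the need for certain drugs (e.g., antiemetics, antipyretics, analgesics, diuretics, and electrolytes"). Section 3.3.2 compares the number of complications between the groups on the day of operation and at 1, 6 and 12 months.

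**The concern.** The form an event goes on depends on what the site thinks caused it, and one of the possible causes exists in only one arm. Besides "Anaphylaxis (especially in those with iodine or shellfish allergies"), the ICG risks listed in section 8.2.1 are urticaria, cough, nausea, itch and rash. Several of these also occur after any operation. In the FGS arm an early post-operative event of this kind has two possible destinations. In the control arm it has one at most. The person choosing knows the allocation.

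If FGS events ascribed to ICG are kept off the complications eCRF, minor complications are undercounted in that arm alone. Complications are a between-arm secondary outcome, so FGS would look somewhat safer than it is. Because this happens when data are captured, the analysis may not be able to put it right. Section 9.2 requires grading for complications but says nothing of grading entries on the AE eCRF.

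**Working it through.** **1. Do the two routes overlap in time?** Inputs are the 72-hour window (section 9.2) and the lead time of 12 to 24 hours (section 8.1.2).

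- ICG given 24 h before: 72 − 24 = 48 h from the start of the procedure (48/72 = 67%).
- ICG given 12 h before: 72 − 12 = 60 h from the start of the procedure (60/72 = 83%).

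Most of the ICG window therefore falls during or after surgery, when complications are also being recorded.

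**2. Where does a non-serious event in that overlap go?** Take nausea needing an antiemetic, or a rash.

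- *Control.* No ICG was given, so the AE eCRF cannot apply. The event goes on the complications eCRF if the PI judges it a complication of surgery. Otherwise it is recorded nowhere.
- *FGS, ascribed to surgery.* Complications eCRF.
- *FGS, ascribed to ICG.* AE eCRF. Nausea, itch, rash and cough are not among the examples in section 3.2.2, so they enter only through the catch-all. An event that the PI puts down to the dye does not fit the catch-all's wording. No rule requires it on the complications eCRF as well.
- *FGS, possibly either.* It meets both descriptions, and section 9.2 gives no rule.

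**3. How large could the effect be?** The protocol states no complication rate, so there is no figure to reproduce. The following is an illustration on assumed inputs. Let p be the true proportion of patients with a complication, equal in both arms. Let f be the share of FGS patients with a complication who are no longer counted. The observed FGS proportion is q = p(1 − f), the spurious difference is p − q, and with 250 per arm SE = √[p(1 − p)/250 + q(1 − q)/250]. The error is that of a two-sided 5% z-test.

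| p | f | q | Difference (points) | Odds ratio | Two-sided error |
|---|---|---|---|---|---|
| 20% | 2% | 19.6% | 0.4 | 0.98 | 5.1% |
| 20% | 10% | 18.0% | 2.0 | 0.88 | 8.8% |
| 30% | 2% | 29.4% | 0.6 | 0.97 | 5.2% |
| 30% | 5% | 28.5% | 1.5 | 0.93 | 6.6% |
| 30% | 10% | 27.0% | 3.0 | 0.86 | 11.5% |
| 50% | 10% | 45.0% | 5.0 | 0.82 | 20.2% |

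Worked line, p = 30% and f = 10%: q = 0.30 × 0.90 = 0.27; SE = √(0.00084 + 0.00079) = 0.040; 0.03/0.040 is about 0.74 standard errors.

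If sites enter such events on both forms, f = 0: the difference is 0, the odds ratio 1.00 and the error 5%.

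**The case against.** The strongest reply is that section 9.2 never makes the forms mutually exclusive. Its restriction limits what enters the AE eCRF and removes nothing from the complications eCRF. That is correct. A reader might infer that the comparison *is* biased, but the text supports only that it could be, depending on site practice. The risk remains because separate recording by cause, together with the surgical wording of the catch-all, lets a site drop such an event without deviating from the protocol.

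Other points on that side also stand:

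- A reader might infer that the same event in a control must be a complication. It counts only if the PI so judges it. If not, no bias towards FGS arises from that event.
- Sections 9.2 and 9.3.1 capture SAEs in both arms, so the issue is mainly minor events. The SAE window opens earlier for FGS, which would count against FGS.
- Reactions between injection and surgery are not surgical complications. Recording them apart is right.
- The Trial Summary takes complications from the clinical notes, and AE eCRF entries are kept, so an analysis might add some back. That would need a rule, and grading, that section 9.2 does not provide for those entries.

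A much larger effect is also tempting. If 20% to 30% of patients had an early gradable event and 25% to 50% of those in FGS were labelled possibly ICG, the shift would be 5 to 15 points (20% × 25% to 30% × 50%). The documents do not support this. It would mean that 5% to 15% of all FGS patients are recorded as having post-operative ICG reactions. Section 1.2 says that ICG has rarely been linked to adverse events and that the earlier sarcoma and paediatric series had none related to ICG. It also assumes that each relabelled event is that patient's only complication.

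**Conclusion.** The point holds as a risk of differential recording. The protocol routes early events by attributed cause, one route is closed to controls, unblinded staff attribute cause, and about 48 to 60 hours of the ICG window coincide with surgery and early recovery. Non-serious events ascribed to ICG can therefore leave the FGS complication count, and any bias from this would favour FGS.

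Only the 48 to 60 hours come from the documents. The size of the bias cannot be derived from them. The illustrative 0.4 to 3.0 points (p of 20% to 30%, f of 2% to 10%) rest on assumed rates and on sites using the forms as alternatives, and dual entry would bring the bias to zero. The matter concerns a secondary safety outcome and does not touch the UPM analysis. It is still worth settling now, because a minor event left ungraded and off the complications eCRF may not be recoverable at analysis.

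**What to change.** In section 9.2, state the following:

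- Any event with onset from the start of surgery that meets the complication definition or the Clavien-Dindo grading is recorded on the complications eCRF in both arms. It is counted in the outcome whatever its suspected relation to ICG.
- The complications eCRF carries a 'possibly ICG-related' flag.
- For these events the AE eCRF is an additional record. For events between injection and the start of surgery it is the only record, unless the event is serious.

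The catch-all in section 3.2.2 should be worded to match, so that a suspected ICG cause does not by itself disqualify an event. This does not ask for all adverse events to be collected: an event must still qualify as a complication.

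The cost is one wording change and one field, slightly more recording, and some double entry in the FGS arm. Some drug reactions will then count as peri-operative complications; the flag lets them be shown separately. The change removes the arm-dependent routing (f = 0). It does not remove unblinded judgement of what counts as a complication.

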9.3. Recording and Reporting SAEs

For each SAE the following information will be collected:

- Full details in medical terms and case description
- Event duration (start and end dates, if applicable)
- Severity of event
- Narrative of event
- Seriousness criteria
- Intervention information
- Causality in the opinion of the investigator
- Whether the event is considered expected or unexpected in accordance with the approved Reference Safety Information if a causal relationship is suspected. Rationale for expectedness assessment
- Action taken
- Outcome

